### **11.2 WP1 standard comparator system**

The standard whole blood analyser system used in the central Cardiff & Vale Laboratory at University Hospital Wales, Cardiff is the Yumizen 1500 and 2500, and at the satellite laboratory at VCC, Whitchurch, the Horiba Pentra DS120 or similar. These devices are automated high throughput systems capable of approximately 100 tests/hour using approximately 100-200µl sample volume and an autoloader. The systems test for multiple parameters including a 5-part WBC count and require an experienced operator. These systems will be used as the comparator system for evaluation of the OLO System in this trial and will be operated by the routine operator.

### **11.3 Investigational device operation**

Sight Diagnostics will supply two OLO-U1 analysers for the purpose of this trial which will be placed in a suitable location permitting access to the different operators for each WP1 Cohort: i) VCC acute admissions clinic Senior House Officers (SHOs) or nurses to evaluate blood samples donated from Cohort 1 Suspected neutropenic sepsis participants. ii) VCC Phlebotomists to test Cohort 2 'Borderline' neutropenia participant samples.

### **11.4 Compliance**

The OLO System analyser will display a flag or an Error Code if a problem is detected within the system or sample. The Operating Manual includes a trouble shooting guide which includes explanations and recommended actions for each flag or Error Code described. If the Troubleshooting Guide is unable to resolve a persistent problem, the site should contact either the Sight Diagnostic helpdesk using the details provided in the Operating Manual in the first instance, copying in the ADVANCE team at the CTR at [[contact]](mailto:[contact]) who will liaise with the Sight Diagnostics, to resolve the problem.

Some system flags and Error Codes require a replacement finger prick or venous blood sample aliquot to be taken. Consent for taking additional study samples under these circumstances for the purposes of WP1 will be included in the relevant WP1 Participant PIS/ICF.

The ADVANCE database will include fields to permit the collection and analysis of device flags, Error Codes, and sample re-takes.

The CTR will review the ADVANCE database to assess compliance to the WP1 investigational device operating procedures and protocol approximately halfway through the predicted device assessment phase.

Any non-compliances to the WP1 sections of the Protocol identified at site will be reported by the site to the CTR immediately and followed up by the CTR following the CTR GCP/Protocol Non-Compliances and Serious Breaches SOP Where appropriate, a triggered site visit may be conducted by the CTR.

## 12 Trial procedures

### 12.1 WP1: Cohort comparator study

#### 12.1.1 ..... WP1 screening assessments

On average we anticipate participants will participate in WP1 for a period of up to one month from the date of registration to the end of trial follow up. There will be no cost to the participant for participating in the trial. Participants will not be paid for participating in the trial. The participant will not be required to have any additional medical checks or medication, or attend the hospital more frequently, during the course of the study than they would if they do not participate.

The Participant must not be given the relevant WP1 PIS/ICF until after the routine non-trial assessments, treatment and sample collections for the relevant cohort have been completed as specified in Section 9.

After taking written informed consent, but before registering a patient in the study, the patient's healthcare professional will collect some screening information to confirm they are eligible to take part in the study (See Section 9.4).

#### 12.1.2 ..... WP1 trial-specific blood sample collection

Following registration, the following study blood samples will be collected from each participant for testing using the investigational device from participants recruited to Cohort 1 or 2:

1x 30µl new study sample of whole blood collected using the finger prick method and a Prolance Max Flow Lancet (or suitable locally or externally sourced alternative) and transferred to a OLO (disposable cartridge using the method described in the OLO System Operating Manual (i.e. 1 replicates).

OR

1x 700µl new study sample aliquot taken from a previously collected routine K2EDTA venous blood tube sample using the blood tube dispensers provided.

A second study sample (new fingerprick or existing venous sample aliquot) will be collected if the original study sample results in a test result error.

Study samples will be tested using the OLO (Analyser following the instructions provided in the OLO- Operating Manual [31], before the participant is discharged from hospital. The test result will be obtained <10 minutes after inserting the microcuvette into the analyser.

Consent and sample collection must be initiated as soon as possible after completion of the standard non-trial assessments, treatment and sample collections.

Study samples must not be removed from routine venous samples until the sample has stood for **at least 20 minutes**. If this process will prevent the routine sample from reaching the routine laboratory within the required local and/or national permitted timeframe a finger prick sample must be taken instead.

Samples tested in the OLO (Sight Diagnostics) analyser will be destroyed following local hospital procedures immediately following conduct of the study test. The samples will not be stored for future research.

The participant and their treating hospital consultant will only be told the results from their standard care tests. The result from the study tests will **not** be used to manage the participant.

If the standard care test(s) show that the participant has neutropenic sepsis their treating hospital consultant will decide what treatment they need (for example whether or not they need to continue taking antibiotics, stay in hospital, or can be discharged) in discussion with the participant and following local standard procedure.

### **12.1.3 .....ADVANCE Qualitative Acceptability Survey**

Prior to discharge from the hospital, Cohort 3 participants will be given a paper copy of the ADVANCE Survey [33] to complete about their views around the study and our intended use of the new equipment

The healthcare professional will ask the patient to complete the survey before they leave the hospital following their discharge. The survey will take about 30 minutes for the participant to complete. Completed surveys will be handed to the local PI.

**12.1.4 ..... Baseline toxicity data**

Baseline toxicity data will be collected after consent and prior to collection and analysis of study blood samples. SAEs must be reported following the timeframes and procedures specified in Section 13.

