#### **6.1.3 Acceptability survey**

Participants in a third cohort (WP1 Cohort 3; n=24) will be given an anonymous survey to complete during their hospital in-patient visit. Participants will be asked to return the completed survey to their healthcare worker prior to leaving the hospital.

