Patients may be identified and invited to participate in the survey by members of the routine treatment team at Velindre Cancer Centre who have been informed of the ADVANCE study. Surveys will not request personal identifiable or special 'clinical' data, thus Cohort 3 participants will not be required to provide formal written consent and anonymous data will be collected under. The survey will include a brief written invite explaining that by completing and returning the survey the participant is providing implied consent. .

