## **9.5 Registration**

WP1-3 participants will not be randomised.

WP1 Cohort 1 and 2 participants will be registered on the ADVANCE electronic trial database or a backup electronic registration list by a member of the local site team who has been delegated the responsibility of registration on the ADVANCE Site Staff Delegation Log. The database or back up list will require confirmation of the eligibility criteria before allocating a unique trial participant identification number to identify the participant.

The participants General Practitioner (GP) will be notified of the participants enrolment in ADVANCE using the ADVANCE GP Letter, if the participant gives consent to do so by initialling a separate box on the WP1 ICF.

WP1 Cohort 3 participants will be registered anonymously on an excel spreadsheet by the participating site.

WP2 and WP3 participants will be registered by the group discussion meeting leader on the WP2 and WP3 Screening Logs [23-24] respectively.

WP1-3 participants are permitted to be recruited to other clinical trials without prior discussion with the ADVANCE CI or the CTR.

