**Table 2. Schedule of enrolment, device and comparator interventions and assessments for WP1 **

	Non-Trial Assessments	Informed Consent	Screening Assessment	Trial registration	Assessment 1 Baseline	Assessment 2 Follow Up
Days	0	0	0	0	0	14-28
Hours	0-5	0-5	0-5	0-5	0-5	N/A
All Cohorts						
Given relevant WP1 PIS/ICF 	X					
Informed consent 		X				
Eligibility assessment (including review of medical history and triage data for relevant cohorts)			X			
Trial registration				X		
Withdrawal as applicable					X	X
Cohort 1 Only						
Routine telephone triage	X					
Routine hospital admission for suspected neutropenic sepsis, inclusive of routine non-trial assessment, antibiotic treatment and venous blood sample collection	X					
Cohort 2 Only						
Routine attendance at phlebotomy for routine pre-chemotherapy or paclociclib assessment, including repeat white blood cell count due to prior 'borderline' neutropenia test result	X					
Cohort 1 and 2 Only						
Baseline toxicity assessment					X	
Collect finger prick or venous K 2 EDTA study blood sample and analyse using OLO System 					X	
SAE safety assessment 					X	X
Enter standard test, antibiotic treatment, hospital discharge and follow up data on ADVANCE database					X	
Collection of follow up data as applicable						X
Cohort 3 Only						
Given WP1 Cohort 3 Anonymous Acceptability Survey					X	
Complete and return Acceptability Survey prior to discharge 						X

 Taken from the HRA CTIMP protocol template (2016).

 Must be taken and analysed before the participant is discharged from hospital.

 Baseline toxicity data to be collected after consent and prior to collection and analysis of study blood samples. SAEs must be reported following the timeframes and procedures specified in Section 13.

 Participants should be reminded to return their survey prior to leaving the hospital following discharge..

 Participant must not be given the relevant WP1 PIS/ICF until after the standard non-trial assessments, treatment and sample collections have been completed.

 Consent to be taken after completion of routine neutropenic sepsis assessments and starting antibiotics for Cohort 1 participants.

### **12.1.5 ..... Baseline and follow up assessments**

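### The anonymous Cohort 3 survey is handed back to the treating and study team with no stated safeguard at hand-in, which may tilt answers towards acceptability

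*Protocol*

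**What the plan says.** Four features of the survey are fixed in the protocol.

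- **Who invites.** Section 9.1.1 (Cohort 3): "Patients may be identified and invited to participate in the survey by members of the routine treatment team at Velindre Cancer Centre".
- **What is asked.** Section 12.1.3 gives the patient a paper form "to complete about their views around the study and our intended use of the new equipment".
- **How it comes back.** Section 6.1.3: "Participants will be asked to return the completed survey to their healthcare worker prior to leaving the hospital". Section 12.1.3: "The healthcare professional will ask the patient to complete the survey before they leave the hospital following their discharge", followed by "Completed surveys will be handed to the local PI". Table 2, footnote 4: "Participants should be reminded to return their survey prior to leaving the hospital following discharge".
- **How anonymity is provided.** Section 9.1.1: "Surveys will not request personal identifiable or special 'clinical' data". Section 9.5: "WP1 Cohort 3 participants will be registered anonymously on an excel spreadsheet by the participating site".

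Section 9.1.1 gives the absence of identifying and clinical data as the reason why no formal written consent is taken. Section 10.1 adds that a submitted survey cannot be withdrawn. The lay summary (3.2) and section 6.2 say that the survey answers will be used to judge whether the device is acceptable to patients.

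**The concern.** Anonymity does two jobs in a survey of this kind. It protects the stored record, and it lets the respondent speak freely when completing and returning the form. The protocol's provisions cover the first. The second depends on what happens at hand-in, and there the form passes to people who know the patient, at the site where the device is being evaluated and where the patient is being treated.

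Respondents who expect their carers to see their answers tend to be more favourable. The likely direction is therefore towards acceptability, which is the quantity the survey is meant to inform. Anonymity also stands in for written consent in this cohort, and a submitted form cannot be withdrawn. Both are reasons to protect the moment of return as well as the data file.

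**Working it through.** This is a point of procedure, so most of the check consists of setting the sections side by side.

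**Step 1: follow the form.**

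| Stage | Who is involved | Where stated |
|---|---|---|
| Invitation | Routine treatment team | 9.1.1, Cohort 3 |
| Request to complete | Healthcare professional, before the patient leaves | 12.1.3 |
| Reminder to return | Before the patient leaves; person not named | Table 2, footnote 4 |
| Return | Patient's own healthcare worker | 6.1.3 |
| Onward | Local PI | 12.1.3 |
| Registration | Participating site, anonymously | 9.5 |

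Every named handler up to and including the PI belongs to the care or study team. No sealed, postal, online or third-party route appears.

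**Step 2: do the two recipients conflict?** Section 6.1.3 says what the patient does. Section 12.1.3 is in the passive and does not say who hands the forms to the PI. The two fit together as a chain: patient to worker, worker to PI. They are not contradictory, but the chain is left to be inferred.

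**Step 3: what is exposed?** The form carries no identifiers and registration is anonymous, so the dataset need not be linkable to a person. The worker who takes the form from the patient does know whose it is.

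**Step 4: reproduce the only figures attached to this survey.** Section 14.1.1 plans 24 approached and 19 returned, with a 95% interval of 59.5% to 90.8%. The Wilson interval is

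[p + z²/2n ± z√(p(1−p)/n + z²/4n²)] / (1 + z²/n).

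With p = 19/24 = 0.7917, n = 24 and z = 1.96:

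- p + z²/2n = 0.7917 + 0.0800 = 0.8717
- z√(0.006872 + 0.001667) = 0.1811
- 1 + z²/n = 1.1601
- limits: 0.6906/1.1601 = 59.5% and 1.0528/1.1601 = 90.8%

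This matches. The stated widest interval, 31.4% to 68.6%, is the Wilson interval for 12/24. Both figures concern the return proportion. Neither concerns favourable answers, and the point made here does not depend on them.

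**Step 5: sensitivity, for illustration only.** The protocol gives no expected share of favourable answers. Assume 15 of 19 returned surveys are favourable, and that k of those 15 were given out of courtesy:

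| k | Share without them | Wilson 95% interval |
|---|---|---|
| 0 | 15/19 = 78.9% | 56.7–91.5% |
| 1 | 14/19 = 73.7% | 51.2–88.2% |
| 3 | 12/19 = 63.2% | 41.0–80.9% |
| 5 | 10/19 = 52.6% | 31.7–72.7% |

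Each such answer is worth 1/19 = 5.3 points. The value of k is unknown. The table shows how sensitive a sample this small is and does not estimate the bias.

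**The case against.** The strongest reply is that nothing stated is wrong. No endpoint or decision rule is shown to fail, the form has no identifiers, and return before leaving is a sensible way to secure the 80% return that the feasibility study is testing. Handling details could also sit in the survey invite, the Qualitative Analysis Plan or the Data Management Plan, which are not to hand. Most of this stands and keeps the point small. It does not remove it: the protocol itself fixes who takes the form back, and a sealed envelope is compatible with on-site return.

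A reader might infer more than the text supports:

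- **That the protocol gives two conflicting routes, or has the patient hand the form to the PI in person.** Step 2 shows a chain; only the return to the healthcare worker is stated as the patient's act.
- **That anonymity of the data is broken.** It is not. What is unprotected is confidentiality towards staff at hand-in. Nor does the protocol say that forms are open or read on receipt; it is silent.
- **That the treating team promotes the device.** Section 9.1.1 says only that the team has been told about the study. Cohort 3 patients have not had blood tested on the device, so they are not rating something these staff did to them, which weakens the courtesy argument.
- **That favourable answers could carry the study forward.** The acceptability outcomes listed in section 5.3 come from the discussion groups. In Table 7 acceptability is judged on focus group data, and the survey criterion is the return rate.
- **That the bias is some definite number of percentage points.** Any such figure rests on an assumed number of courtesy answers.

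**Conclusion.** The point holds as a minor design weakness. A survey presented as anonymous is returned to the patient's own healthcare worker and passed to the local PI, and the protocol states no safeguard at that moment. The probable direction of any effect is towards acceptability; its size is unknown. The conclusion rests on two assumptions: that patients answer less freely when their care team collects the form, which is a general methodological inference, and that no safeguard is provided in the unseen survey documents. If one is, the protocol wording should still be brought into line with it. The practical reach is confined to the descriptive use of the answers described in sections 3.2 and 6.2.

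**What to change.** State one route, in the same words, in section 6.1.3, section 12.1.3 and Table 2 footnote 4: the patient seals the completed form in an unmarked envelope and returns it on site before leaving, either to a collection box or to the healthcare worker, and the envelope is opened only by the trials unit. The sentence sending completed surveys to the local PI should be replaced accordingly.

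Keep the anonymous Cohort 3 log and registration in sections 9.2.1 and 9.5, and have them record the numbers issued and returned. The 80% criterion in Table 7 can then still be computed as surveys returned divided by surveys given out, with the trials unit confirming on opening that each form was completed.

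The cost is envelopes, possibly a box, a few sentences of protocol text and minor handling by the trials unit. One small loss is that site staff can no longer check a form for completeness on receipt.

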**Table 2. Schedule of enrolment, device and comparator interventions and assessments for WP1 **

	Non-Trial Assessments	Informed Consent	Screening Assessment	Trial registration	Assessment 1 Baseline	Assessment 2 Follow Up
Days	0	0	0	0	0	14-28
Hours	0-5	0-5	0-5	0-5	0-5	N/A
All Cohorts						
Given relevant WP1 PIS/ICF 	X					
Informed consent 		X				
Eligibility assessment (including review of medical history and triage data for relevant cohorts)			X			
Trial registration				X		
Withdrawal as applicable					X	X
Cohort 1 Only						
Routine telephone triage	X					
Routine hospital admission for suspected neutropenic sepsis, inclusive of routine non-trial assessment, antibiotic treatment and venous blood sample collection	X					
Cohort 2 Only						
Routine attendance at phlebotomy for routine pre-chemotherapy or paclociclib assessment, including repeat white blood cell count due to prior 'borderline' neutropenia test result	X					
Cohort 1 and 2 Only						
Baseline toxicity assessment					X	
Collect finger prick or venous K 2 EDTA study blood sample and analyse using OLO System 					X	
SAE safety assessment 					X	X
Enter standard test, antibiotic treatment, hospital discharge and follow up data on ADVANCE database					X	
Collection of follow up data as applicable						X
Cohort 3 Only						
Given WP1 Cohort 3 Anonymous Acceptability Survey					X	
Complete and return Acceptability Survey prior to discharge 						X

 Taken from the HRA CTIMP protocol template (2016).

 Must be taken and analysed before the participant is discharged from hospital.

 Baseline toxicity data to be collected after consent and prior to collection and analysis of study blood samples. SAEs must be reported following the timeframes and procedures specified in Section 13.

 Participants should be reminded to return their survey prior to leaving the hospital following discharge..

 Participant must not be given the relevant WP1 PIS/ICF until after the standard non-trial assessments, treatment and sample collections have been completed.

 Consent to be taken after completion of routine neutropenic sepsis assessments and starting antibiotics for Cohort 1 participants.

### **12.1.5 ..... Baseline and follow up assessments**

During participation in the study we will collect information about the patients suspected neutropenic sepsis, antibiotic treatment, hospital discharge, and follow up from their medical records and other data systems (for example, CANISC, Chemocare, local UKONS ACCESS-based spreadsheet) held within Velindre University NHS Trust.

If the patient develops a new medical condition, or an existing condition worsens during participation in the study or at a withdrawal visit, then the healthcare professional may contact the patient and ask them about this, until it has completely resolved.

### **12.1.6 ..... Investigation device test results**

The results of the investigational device blood tests will not be shared with the participant or used to manage the treatment pathway of the patient. The treating consultant will be told the results of the study tests after the participants condition has been successfully treated so that we can find out if it would have changed how the participant was treated. We intend to use the results of this feasibility study to inform the development of a larger UK-wide randomised study in which we intend to use the results of the investigational device(s) to manage patient pathways.

### **12.1.7 ..... Review of existing neutropenic sepsis data held at site**

The VCC Service Improvement team conducts regular audits of UKONS neutropenic sepsis data to meet UK UKONS reporting requirements. The team will provide existing clinical data routinely collected from the type of patient eligible for WP1 Cohorts 1 and 2 to the CTR for analysis and review in parallel to the WP1 device cohort study data. Fully anonymised audit data will be transferred to the CTR following CTR and Sponsor data protection guidance and procedures, and analysed alongside the other WP1 and WP2-3 data by the Statistician.

## **12.2 WP2: Patient/carer discussion group meeting**

Up to 20 members of the VPLG will be invited to participate in WP2 and given a copy of the ADVANCE WP2 PIS/ICF [26] by the recruiting VPLG Co-ordinator as specified in Section 9. The member will be

asked to return the reply slip on page 2 of the document by email or post to the VPLG Co-ordinator. Members who decline to take part must not be contacted further by the recruiting VPLG Co Ordinator for the purposes of the trial. The recruiting VPLG Coordinator will liaise with the VPLG member and the ADVANCE Trial Manager to arrange attendance at a discussion group meeting to be held at VCC in Cardiff, UK or a suitable alternative location at the University of Wales Hospital, Heath Site or Cardiff University, at a specified future date and time, or using a virtual video conferencing platform if required.

